5.4 Exclusion Criteria

Potential participants who meet the following criteria will be excluded from the study:

- 1. Has any condition that, in the opinion of the Investigator of Record (IoR)/designee, would preclude informed consent, make study participation unsafe, complicate interpretation of study outcome data, or otherwise interfere with achieving the study objectives.
- 2. For currently or recently pregnant or breastfeeding women: known HIV-positive status, verified per recent health record (e.g., health passport, ante-natal book, HIV test card, or similar document) or by self-report if health record(s) not available.

6 STUDY PRODUCT

MTN-041 will not involve the administration of any study product.

7 STUDY PROCEDURES

7.1 Focus Group Discussions

Up to 200 men and women will be enrolled into MTN-041 for FGD participation (see Section 10.3.1 for sample composition details). Enrolled participants will be assigned into groups based on gender (male or female), role (grandmothers) and/or other characteristics (e.g., age, education, microbicide/PrEP exposure). Sites may assign participants into groups based on these characteristics after consultation with the MTN-041 Management Team if it is deemed that this categorization is both feasible and informative at the site(s). Final group designation at each site will be dependent on adequate sample size and representativeness of the recruitment pool.

Enrolled participants will be asked to complete a single FGD (with other participants in the same group assignment). Sites may ask enrolled participants to complete a single IDI instead of an FGD after consultation with the MTN-041 Protocol Team. The decision to conduct an IDI instead of an FGD will be dependent on adequate sample size and scheduling feasibility. The IDIs will also focus on individual and community perceptions of the topics listed above. Prior to completing the FGD (or IDI), enrolled participants will receive an introduction to the VR and oral PrEP using standardized materials.

Note: Specific information regarding group designation and assignment of enrolled participants to an IDI instead of an FGD will be specified in the MTN-041 SSP Manual, available at http://www.mtnstopshiv.org/studies.

7.1.1 Screening and Enrollment (Focus Group Discussions) – Administrative, Behavioral and Regulatory Procedures

Table 1: Screening and Enrollment Procedures - Focus Group Discussions

Screening and Enrollment – Focus Group Discussions				
Component	Procedures			
Administrative and Regulatory	 Confirm eligibility Obtain written informed consent for screening and enrollment Assign a unique Participant Identification (PTID) Number Collect locator information Provide reimbursement for study visit 			
Behavioral	 Provide introduction to VR and PrEP via standardized materials Administer demographic and behavioral questionnaire(s) Conduct Focus Group Discussion (FGD) or in-depth interview (IDI) 			

Multiple visits may be conducted to complete all required procedures, if necessary.

7.2 Key Informant Interviews

Up to 40 KIs will be enrolled into MTN-041 (see Section 10.3.2 for sample composition details). A single IDI will be conducted with each enrolled participant. Prior to completing the IDI, enrolled participants will receive an introduction to the VR and oral PrEP using standardized materials.

7.2.1 Screening and Enrollment (Key Informant Interviews) – Administrative, Behavioral and Regulatory Procedures

Table 2: Screening and Enrollment Procedures – Key Informant Interviews

Screening and Enrollment – Key Informant Interviews				
Component	Procedures			
Administrative and Regulatory	 Confirm eligibility Obtain written informed consent for screening and enrollment Assign a unique PTID Number Collect locator information Provide reimbursement for study visit 			
Behavioral	 Provide introduction to VR and PrEP via standardized materials Administer demographic and behavioral questionnaire(s) Conduct in-depth interview (IDI) 			

Multiple visits may be conducted to complete all required procedures, if necessary.

7.3 Behavioral Evaluations

The study will address questions related to the primary and secondary objectives of intravaginal product and oral medication acceptability facilitators and challenges experienced by pregnant and breastfeeding women, from the perspective of community members, including KIs such as HCPs and TBAs. The study will also explore community members' preferences related to HIV prevention methods for pregnant and breastfeeding women, and acceptable approaches to educate and market HIV prevention methods such as VRs and oral PrEP in this population. These questions will be assessed via behavioral questionnaires and either FGDs or IDIs conducted by trained interviewers/facilitators.

Additional questions and probes will be designed to delve further into the social and cultural norms that may play a role more broadly in product use acceptability and preferences for pregnant and breastfeeding women.

7.3.1 Behavioral Questionnaires

Demographic and behavioral questionnaires will be used to inform different dimensions of data collected during the FGDs and IDIs.

7.3.2 In-Depth Interviews (IDIs) and Focus Group Discussions (FGDs)

Both FGDs and IDIs will include, but not be limited to, topics such as:

- Perceptions of acceptable and/or typical vaginal and sexual practices during pregnancy and breastfeeding, including contraceptive use (when relevant)
- Perceived safety and acceptability of taking medications, oral or otherwise, during pregnancy and breastfeeding, for both the mother and the unborn fetus or breastfeeding infant

- Perceived norms related to women's autonomy and agency during pregnancy and breastfeeding, including the extent to which pregnancy may be medicalized in the community
- Perceived role of male partners in women's decision-making during pregnancy and breastfeeding, including how to engage them in efforts to scale up product roll-out and uptake
- Community beliefs and practices considered taboo or encouraged about pregnancy, childbirth and breastfeeding
- KI beliefs about pregnancy, childbirth and breastfeeding, including specific practices they encourage or discourage
- Attitudes and understanding of VR and oral PrEP efficacy and the concept of partial efficacy
- Socio-cultural context of risk behaviors (including sexual activity) and risk perceptions over time (before, during and after pregnancy), including concerns for the unborn fetus and/or breastfeeding infant
- Main challenge(s) perceived with VR and oral PrEP use during pregnancy and breastfeeding, including product uptake, storage, feasibility of continued product use, drug delivery modality and product attributes
- Main factor(s) perceived to facilitate VR and oral PrEP use during pregnancy and breastfeeding, including product uptake, storage, feasibility of continued product use, drug delivery modality and product attributes
- Other factors (e.g., situational, relationship, trial-specific, social/cultural/economic, sex related, contraceptive methods or other medications, etc.) perceived to influence VR and oral PrEP use patterns during pregnancy and breastfeeding
- Suggestions for recruiting and advertising research study participation to pregnant and breastfeeding women

FGD and IDI guides will be developed by qualified social scientists and administered by qualified interviewers in one of the study languages. Guides will contain questions and suggested probes relating to the main topics of interest. Interviews and discussion sessions will be audio-recorded.

Various tools may be used to facilitate interviews and discussion of sensitive topics with both FGD and IDI participants. These may include, but not be limited to, product facsimiles, video, pictures or show-cards listing topics and themes previously elicited in other studies.

8 ASSESSMENT OF SAFETY

MTN-041 does not involve a study product nor involve clinical, laboratory or other procedures associated with significant risk to participants. Therefore, the only anticipated risks as a result of study participation are social harms and embarrassment when discussing sensitive issues; see Sections 8.2 and 13.4.1 for additional details.

8.1 Safety Monitoring

Site IoRs are responsible for continuous close safety monitoring of all study participants, and for alerting the protocol team if unexpected safety events occur. Study sites will have written procedures for ensuring prompt reporting to the IRB/EC of any unanticipated problem involving risks to subjects or others. No safety events will be captured in the study database. Untoward

clinical or medical occurrences reported by study participants to have been experienced during study participation will be managed appropriately and recorded in participant file notes.

There will be no expedited AE reporting in this study since there are no study products for which to report AEs.

8.2 Social Harms Reporting

Although study sites will make every effort to protect participant privacy and confidentiality, it is possible that participants' involvement in the study could become known to others and that social harms - non-medical adverse consequences - may result. For example, participants could be treated unfairly, or could have problems being accepted by their families, partners and/or communities. Social harms that are judged by the IoR/designee to be related to study participation will be reported to the DAIDS Medical Officer (MO), Protocol Chairs, and responsible site ECs/IRBs according to their individual requirements beginning at the time of enrollment (i.e., after a participant signs the informed consent and eligibility is confirmed) until study participation is complete. In the event that a participant reports social harm, every effort will be made by study staff to provide appropriate care and counseling to the participant, and/or referral to appropriate resources for the safety of the participant as needed. Each site will provide such care and counseling in accordance with standardized guidance provided in the MTN-041 SSP Manual. While maintaining participant confidentiality, study sites may engage their CABs in exploring the social context surrounding instances of social harm. Additionally, a Standard Operating Procedure (SOP) for emergency procedures will be developed for the MTN-041 site staff to be used in situations of social harm and when situations that require immediate attention are identified, including domestic violence and suicidal ideation or behavior. The SOP will provide clear guidelines for site staff to refer participants in these situations to the relevant institution/body and to provide feedback to the protocol team.

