4.4 Expected Duration of Participation

The total duration of study participation for each participant is not anticipated to exceed 6 hours, including administrative and data collection procedures. However, the duration of participation is dependent upon the scheduling of IDIs or FGDs. Each IDI is not anticipated to exceed 2 hours and each FGD is expected to take up to 4 hours. Multiple visits may be conducted to complete all required procedures, if necessary.

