13.4 Risk Benefit Statement

13.4.1 Risks

It is not expected that this trial will expose human subjects to unreasonable risk. Participation in research includes the risks of loss of confidentiality and discomfort with the personal nature of questions when discussing study-relevant behaviors, including vaginal and sexual practices, HIV prevention methods and microbicide use.

Psychological Harms

MTN-041 will ask questions that may cause individuals discomfort given their personal nature. Stress and feelings of guilt or embarrassment may arise simply from thinking or talking about one's own behavior or attitudes on sensitive topics. This could result in undesired changes in thought and emotion.

While the risk of psychological harm is anticipated to be minimal, and study staff will inform participants that they can choose not to answer questions at any time, study staff will collect information on participants who report a change in mood as a result of study participation. In addition, study staff will ensure that participants have access to proper clinical resources to address psychological harms.

All FGD participants will be asked and strongly encouraged to respect each other's confidentiality, but participants who take part in the FGDs may still disclose what other participants said during the group discussion. Furthermore, all FGD participants will be asked to use pseudonyms for themselves and for anyone they may talk about during the course of the FGD.

Social Harms

Although study sites make every effort to protect participant privacy and confidentiality, it is possible that participants' involvement in the study could become known to others, and that social harms may result (i.e., because participants could become known as HIV-positive or at "high risk" for HIV infection). For example, participants could be treated unfairly or discriminated against, or could have problems being accepted by their families and/or communities.

Data on the occurrence of potential social harms will be collected from all participants. These data will be captured via CRF and analyzed on an ongoing basis. The protocol team will monitor, evaluate and adjust operations to reduce the potential for such occurrences.

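### Section 8.2 ends onward reporting of social harms when participation ends, so most of the harms the protocol anticipates would probably fall outside it

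*Protocol*

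**What the plan says.** Section 8.2 requires social harms that the investigator judges related to participation to be reported to the DAIDS Medical Officer, the Protocol Chairs and the responsible ethics committees, "beginning at the time of enrollment (i.e., after a participant signs the informed consent and eligibility is confirmed) until study participation is complete".

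Section 4.4 gives the expected length of participation: "The total duration of study participation for each participant is not anticipated to exceed 6 hours, including administrative and data collection procedures". It adds "Each IDI is not anticipated to exceed 2 hours and each FGD is expected to take up to 4 hours", notes that "the duration of participation is dependent upon the scheduling of IDIs or FGDs", and allows for more than one attendance: "Multiple visits may be conducted to complete all required procedures, if necessary".

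Sections 7.1 and 7.2 plan a single focus group discussion (FGD) or a single in-depth interview (IDI) per person. Tables 1 and 2 list the procedures. Neither lists a contact after the session or a social-harm assessment.

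Section 13.4.1 says that data on potential social harms will be collected from all participants, and continues: "These data will be captured via CRF and analyzed on an ongoing basis". The stated purpose is for the protocol team to monitor such events and adjust operations. Section 8.1 says "No safety events will be captured in the study database". Section 11.1 says that case report forms (CRFs) are double-entered in an electronic database.

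**The concern.** Section 8 names social harms and embarrassment as the only anticipated risks of taking part. The social harms described in Sections 8.2 and 13.4.1 share a mechanism: others learn that the person took part, or an FGD member repeats what was said, and family, partner or community then react. That reaction would usually come after the participant has gone home, when participation as the protocol uses the word is over.

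If so, the reporting rule covers mainly the time before the anticipated harm would show itself. A participant who told the site about rejection by her family a week later could be offered care and counselling, but Section 8.2 would not require the report to go further. A low count in the Section 13.4.1 data would then reflect the length of the window as much as the absence of harm, and the team would have less to act on than the section promises.

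The second matter is where these data go. A site that reads the Section 8.1 sentence on the study database broadly could leave social harms out of it, while another site follows Section 13.4.1 and enters them.

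**Working it through.** The point rests on comparing passages. There is no sample-size, error-rate or event-count figure to reproduce.

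**Step 1: when the window closes.** Section 8.2 closes it when participation is complete. Section 4.4 uses the same notion of participation and anticipates a total of 6 hours or less. That figure is a planning estimate which the protocol does not derive. It is compatible with the session lengths: an FGD of up to 4 hours leaves 6 − 4 = 2 hours for consent, the questionnaire and other procedures, and an IDI of up to 2 hours leaves 6 − 2 = 4 hours.

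**Step 2: what the 6 hours measures.** It is a sum of procedure time. The window in Section 8.2 runs in calendar time. If consent and the session fall on different days, the window is longer than 6 hours. The protocol sets no maximum gap between visits, so the calendar length cannot be computed.

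**Step 3: contacts after the session.** None is listed in Table 1 or Table 2. Locator information is collected, but no later use of it to ask about harms is described.

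**Step 4: when the anticipated harms arise.**

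| Harm or route named | Where | Likely timing |
|---|---|---|
| Involvement becomes known to others | 8.2, 13.4.1 | Possible through attendance, but mostly afterwards |
| FGD members repeat what others said | 13.4.1 | Afterwards |
| Unfair treatment, or problems with acceptance by family, partner or community | 8.2, 13.4.1 | Follows from the two above |
| Discomfort while discussing sensitive matters | 8, 13.4.1 | During the session |

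The first three rows are the social harms. The last is the embarrassment and psychological discomfort that the protocol treats separately.

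**Step 5: is there another route for late reports?** Under Section 13.5, consent covers what to do if harms are experienced, with no time limit stated. Section 8.2's provisions on care, counselling, referral and the emergency procedure (which includes feedback to the protocol team) also carry no time limit. None of these extends the duty to report onward to the Medical Officer, the Chairs and the ethics committees. Section 8.1 covers unexpected events and unanticipated problems, whereas social harm is an anticipated risk.

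**Step 6: the database.** Section 13.4.1 sends social harms to a CRF, and Section 11.1 sends CRFs to a database. Whether Section 8.1 stands against this depends on whether a safety event includes a social harm, a term the protocol does not define. The title and opening text of Section 8, which is about safety and names social harms, favour inclusion. Section 8.2 calls social harms non-medical, and the sentence that follows the database statement in Section 8.1 concerns clinical or medical occurrences. Both favour exclusion. Either reading is open to a site.

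**The case against.** The strongest reply is that the window is neither as short nor as empty as it looks. Six hours is an expectation about procedure time, and several visits are allowed. FGDs need roughly 6 to 10 people from one group, so enrolment and session may well fall on different days. Some harm could arise inside the window: through being seen to attend, during the discussion itself, or between visits. All of that stands. A reader might infer that the window is a single visit capped at 6 hours, or that it closes before any anticipated harm is possible. The protocol supports neither.

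A reader might also want to express the window as a percentage of the time at risk. That would need a calendar length for participation and a period of risk after the session. The documents give neither, so any such percentage would rest on assumptions.

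It can further be said that participants are told what to do if harm occurs, and that recruitment runs about 3 to 6 months per site (Section 4.3), so harms heard of early can inform later sessions. Both are true, and the team is not left without any means of adjusting. The consent forms were not available, so a contact route cannot be presumed missing. What remains is that the formal reporting duty stops when participation ends, and nothing in the protocol says that a related harm reported later must be forwarded or put on the CRF.

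Finally, Section 8.1 and Section 13.4.1 can be read together if safety events are clinical events. That reading is reasonable, so a reader who infers an outright contradiction goes further than the text allows.

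**Conclusion.** The concern holds in a limited form. As Section 8.2 is worded, most of the social harms the protocol anticipates would probably appear after reporting has stopped, and the Section 13.4.1 data would understate them. This assumes that harms depending on other people's knowledge and reaction mostly follow the session, which is how the protocol itself describes them, and that no follow-up contact exists beyond Tables 1 and 2.

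The effect is one of direction, towards under-reporting, and cannot be quantified from the documents. It touches participant protection and the operational monitoring the protocol promises. The qualitative objectives and the planned analyses do not depend on a social-harm count.

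The wording of Section 8.1 is an ambiguity over an undefined term, which sites could resolve differently, and it is worth one clarifying phrase.

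**What to change.** - **Section 8.2.** Replace the end of the window, so that onward reporting covers any related social harm that a participant reports to the site from enrolment until site close-out. State that each such report is recorded on the CRF described in Section 13.4.1, and that reports received after the session are labelled as passively reported.
- **Section 8.1.** State that safety events means clinical or medical events, so that the sentence is consistent with CRF capture of social harms in Section 13.4.1 and database entry in Section 11.1.

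The cost is protocol wording and a small number of late forms. No visit is added. The drawback is that passive reports are incomplete. Participants seen early at a site will also have a longer time to report than those seen last, so the count should not be read as a rate over a common period. The label makes that limitation visible.

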9 CLINICAL MANAGEMENT

There are no additional clinical management considerations for participants enrolled in this study. Participants who express concerns with social, psychological or clinical issues will be referred for appropriate care to services available at the CRS, or at nearby partnering facilities.

9.1 Criteria for Early Termination of Study Participation

Participants may voluntarily withdraw from the study for any reason at any time. The loR also may withdraw participants from the study to protect their safety and/or if they are unwilling or unable to comply with required study procedures. Participants also may be withdrawn if the study sponsors, government or regulatory authorities, including the Office for Human Research Protections (OHRP), or site IRBs/ECs terminate the study prior to its planned end date. Study staff members will record the reason(s) for all withdrawals in participants' study records. In the event that participants who voluntarily withdraw from the study wish to re-join the study, they may do so if the accrual target has not yet been met.

10 ANALYTICAL CONSIDERATIONS

10.1 Overview and Summary of Design

MTN-041 is an exploratory study that will utilize FGDs and IDIs to identify individual, interpersonal, social and cultural factors that may affect potential uptake of two safe and effective HIV prevention products, the monthly dapivirine VR and daily oral PrEP, by pregnant and breastfeeding women in Africa.

The main goal of the study is to elicit community perceptions about the use of intravaginal products and oral medications during pregnancy and breastfeeding, including men's, women's, grandmothers', and KI's willingness to use or recommend/support use of a VR or oral PrEP during pregnancy and breastfeeding.

Secondary objectives of the study include the exploration of:

- Potential preference for a VR or oral PrEP during pregnancy and breastfeeding
- Participants' attitudes about and perceptions of sexual activity during pregnancy and breastfeeding, including how a VR or oral PrEP might affect sexual activity and contraceptive use
- Participants' perceptions of HIV risk during pregnancy and breastfeeding
- Community beliefs and practices considered taboo or encouraged during pregnancy and breastfeeding that might affect VR and oral PrEP uptake and use during these periods, including use of oral medications and intravaginal products

